 - For patients undergoing needle biopsy: Images of the procedure will be reviewed to determine if the correct node was biopsied.
 1. If the correct node was biopsied, then a negative biopsy will be considered a False Positive.
 2. If the incorrect node was biopsied, then follow-up imaging as described above will be performed.
- (b) Bone lesions: Given the high rate of false negative biopsies for osseous metastases in patients with prostate cancer, patients with negative bone biopsies of PSMA PET positive lesions will be further evaluated:
- If pathology demonstrates an alternative diagnoses that is known to be PSMA positive (eg Renal Cell Carcinoma metastases, Paget's disease), then this will be considered a False Positive.
 - If pathology is indeterminate, then follow-up imaging as described above will be performed.
- (3) Although not routinely performed during standard practice, immunohistochemical staining for PSMA of tumor specimens (primary and lymph node metastases) may be performed, although not required.
- d) Definitions of True Positive, False Positive, True Negative, and False Negative patients and regions: Pathology will be considered superior to imaging and clinical follow-up when available as described below. Patient and region level classification will be performed for each blinded reader, and be reported separately. The following criteria serve as a guide for interpretation. However not all findings on a lesions, region and patient level can be detailed here and investigators may deviate from these criteria in individual patients. These will be recorded for each interpretation that is not described in this protocol for the definition of a region or patient.
- i) Patient level evaluation:
- (1) True positive patient: A single region in a patient contains a true positive node either by pathology or imaging/clinical follow-up.

- (a) For a patient to be considered a True Positive, only one region is required to have a true positive lesion as described above, unless one region is categorized as a false positive based on pathology. This means that a single pathology false positive region outweighs regions with imaging/clinical follow-up true positive disease.
 - (b) A patient will be considered a True Positive if one region contains a lesion that is True Positive, even if other regions are categorized as inevaluable or false positive based on imaging or clinical follow-up.
- (2) True negative patient: in the absence of True Positive or False Positive lesions, a patient will be considered a True Negative if there is pathology that is negative for disease and corresponding lesion is negative by PSMA PET.
 - (3) False positive patient:
 - (a) Pathology confirms a false positive lesion that is read as positive on PSMA PET.
 - (b) In the absence of pathology: there are no true positive regions, and there is a region that is categorized as false positive based on imaging or clinical follow-up.
 - (4) False negative patient: in the absence of True Positive or False Positive lesions, a patient will be considered a False Negative if there is pathology that is positive for disease and corresponding lesion is negative by PSMA PET. Additionally, patients without evidence of disease on PSMA PET but with biochemical evidence of disease will be considered a False Negative.
- ii) Region level evaluation: Each patient will have four evaluable regions (Table 1: prostate bed, pelvis, extrapelvic soft tissue, and bone metastases). Each region will be categorized as true positive or false positive as described above. Regions without evidence of PSMA positive disease or deemed inevaluable will not be included in the analysis.
 - (1) True positive region:
 - (a) Pathology confirms a PSMA avid lesion as a true positive in the region.
 - (b) In the absence of pathology, clinical or imaging follow-up demonstrates a true positive lesion within the region independent of the presence of an inevaluable lesion or a false positive lesion
 - ie true positive disease will supersede a false positive lesion in the region based analysis if based on imaging/clinical follow-up
 - (2) True negative region: in the absence of True Positive or False Positive lesions within a region, the region will be considered a True Negative if there is pathology that is negative for disease in the region and corresponding lesion is negative by PSMA PET.
 - (3) False positive region:
 - (a) Pathology confirms a PSMA avid lesion as a false positive in the region

- (b) In the absence of pathology, there are no true positive lesions in the region, and there is a false positive lesion by clinical or imaging follow-up.
- (4) False negative region: in the absence of True Positive or False Positive lesions in a region, the region will be considered a False Negative if there is pathology that is positive for disease in the region and corresponding lesion is negative by PSMA PET.

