Of our first cohort of patients, 19% of patients underwent biopsy after a positive PSMA PET imaging. Based on biopsy results there was 100% sensitivity and 87% specificity. There were no True Negatives or False Negatives on biopsy. Imaging follow-up is not complete for our first study so we cannot estimate the percent of patients that will have imaging follow-up, but it appears that roughly 15 to 20% of patients will have imaging follow-up. Consistent with our second protocol, we anticipated that the sensitivity for the four regions and for all regions combined using conventional imaging ranges from 30-60%. An overall sensitivity for ^{68}Ga -PSMA-11 PET of at most 50% will be considered as unacceptably low. Hence, the null hypothesis that the sensitivity is at most 50% will be tested against the alternative hypothesis that the sensitivity is greater than 50%. It is hypothesized that ^{68}Ga -PSMA-11 PET imaging on the per-region and per-patient basis will substantially increase the sensitivity for the four regions to at least 70%. A sample size of 75 true positives is required for rejecting the null hypothesis that the sensitivity is at most 50% with 90% power at the one-sided 0.01 ($=0.05/5$ – a Bonferroni adjustment for evaluating the sensitivity for the four regions and for all regions combined) significance level, assuming an average regions specific prevalence of 20%. Although 19% of patients underwent biopsy and 15% of patients have imaging follow-up, we anticipate that the biopsy rate will fall in this study as referring clinicians become more comfortable with the imaging results. Therefore, we will combine imaging and biopsy follow-up in the primary aim, and will require 375 with both imaging and/or biopsy follow-up in order to power the analysis at a per region level. Assuming a prevalence rate of 20% for disease in each individual region, a total sample size of 1,500 patients is required. In summary, the proposed target accrual of 1,500 patients (375 with biopsies or imaging follow-up) will provide adequate power for detecting the anticipated improvement in the sensitivity for both the per-patient and per-region based ^{68}Ga -PSMA-11 PET imaging. However, a sample size of 107 patients with biopsies/follow-up in total is sufficient for detecting the anticipated improvement in sensitivity when evaluating per-patient based sensitivity.

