8.3.2 Analysis of Primary Endpoints

Sensitivity on a per-patient and per-region-basis of ^{68}Ga -PSMA-11 PET for detection of tumor location confirmed by histopathology/biopsy, clinical and conventional imaging follow-up will be calculated and reported along with the corresponding two-sided 95% confidence intervals. The confidence intervals will be constructed using the Wilson score method. For successful completion of the primary endpoint, two of the three readers will need to have an 70% sensitivity for the detection of disease on a per patient level for the cases that have a) imaging follow-up, b) pathology correlation or c) combination of pathology and imaging follow-up and/or pathology correlation.

^{68}Ga -PSMA-11 PET Results Definition

a) Imaging interpretation ^{68}Ga -PSMA-11 PET:

Local Interpretations: PET images will initially be interpreted by a board certified nuclear medicine physician or a board-certified radiologist experienced in reading PET at the time of the imaging study at the institution that the study is being performed. These interpretations will not be used for final evaluation, and will not be reported as part of the primary or secondary endpoints.

Central Read Logistics: Imaging data will be anonymized and collected at a central site. PET data will be interpreted by three different readers in a random order at separate reading sessions. Cross sectional imaging (CT or MRI) from the ^{68}Ga -PSMA-11 PET will be available for anatomic correlate. The Central readers will be blinded to all other imaging results and all other clinical data.

Reader Positivity and Negativity Definition: Regions defined in Table 1 will be graded for the presence of suspected disease on a two-point scale by each reader (0=Negative or 1=Positive). A region will be judged as positive if at least one lesion in this region is visually positive.

Reader Training: ^{68}Ga -PSMA-11 PET/CT reading training set and guides will be provided and completion of this training will be required for all central review readers. Common pitfalls will be reviewed as part of the reader training.

Criteria for visual interpretation:

Regions of suspected disease will be graded on a two-point scale by each blinded reader (0=Negative or 1= Positive). A region will be judged as positive if at least one lesion in this region is visually positive.

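### The one-sided 0.01 tests against 50% that set the sample size are not carried into the primary analysis, so the four regional sensitivities have no decision rule and only unadjusted 95% intervals

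*Combined protocol and SAP*

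**What the plan says.** Section 8.2.1 (Sample Size and Power Estimate) commits to a hypothesis test: "the null hypothesis that the sensitivity is at most 50% will be tested against the alternative hypothesis that the sensitivity is greater than 50" per cent. The level is one-sided 0.01, obtained as 0.05/5 and described as "a Bonferroni adjustment for evaluating the sensitivity for the four regions and for all regions combined". The size follows from it: "A sample size of 75 true positives is required for rejecting the null hypothesis", with 90% power and an anticipated sensitivity of 70%. At an average regional prevalence of 20% this becomes 375 patients with a reference standard, out of 1,500 enrolled.

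Section 8.3.2 (Analysis of Primary Endpoints) says that the per-patient and per-region sensitivities "will be calculated and reported along with the corresponding two-sided 95% confidence intervals", using the Wilson score method. It then gives one success criterion: two of the three blinded readers must reach 70% sensitivity at the patient level. It mentions no test against 50%, no 0.01 level and no multiplicity adjustment, and it gives no success criterion for any region.

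Per-region sensitivity is nevertheless part of the primary objective (section 2.1) and of the study endpoint (section 8.1).

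**The concern.** The trial was sized to control error across five sensitivity claims, and the section that governs the analysis does not apply that control. An analyst who follows 8.3.2 alone would never use the 0.01 level.

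For the patient-level endpoint a separate and strict rule fills the gap. For the four regions nothing does: the two-sided 95% interval is the only inference that 8.3.2 supplies, and its lower limit corresponds to one-sided 0.025. Section 8.2.1 calls a sensitivity of 50% or less unacceptably low, so 50% is the value a reader will look for in those intervals. A region could then be presented as excluding 50% although it fails the test for which the trial was sized. Section 1.1 intends the data for an NDA submission, so the regional claims should rest on a rule fixed in advance.

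**Working it through.** **Inputs.** From 8.2.1: null sensitivity p0 = 0.50, alternative p1 = 0.70, power 90%, one-sided level 0.05/5 = 0.01, 75 cases per test, 375 patients with a reference standard, and expected disease shares of 15% (prostate bed), 27% (pelvis), 24% (extrapelvic soft tissue) and 11% (bone). From 8.3.2: two-sided 95% Wilson intervals and the 70% per-patient rule. The plan calls the 75 true positives; a sensitivity formula needs diseased cases (true positives plus false negatives), and they are treated so here.

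**1. Reproduce the 75.** One-sample proportion, normal approximation:

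n = [(z(1−α)·√(p0(1−p0)) + z(0.90)·√(p1(1−p1))) / (p1 − p0)]²

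- α = 0.01: [(2.326×0.5 + 1.282×0.458)/0.2]² = 76.6, so 77.
- α = 0.025: [(1.960×0.5 + 1.282×0.458)/0.2]² = 61.4, so 62.

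The stated 75 is within two cases of the first figure and well away from the second. At 75 cases the normal-approximation power is 89.3%. The sample size therefore rests on the adjusted level.

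**2. What each interval demands at 75 cases.** The Wilson lower limit exceeds 50% when x > n/2 + z·√n/2.

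- 95%: 37.5 + 1.960×4.330 = 45.99, so 46/75 (61.3%). Exact P(X ≥ 46 | 75, 0.50) = 3.2%.
- 98%: 37.5 + 2.326×4.330 = 47.57, so 48/75 (64.0%). Exact P(X ≥ 48 | 75, 0.50) = 1.0%; power P(X ≥ 48 | 75, 0.70) = 89.5%.

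A region with 46 or 47 of 75 passes on the 95% limit and fails at the planned level.

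**3. The four regions at the plan's expected shares.** Each share × 375 gives about 56, 101, 90 and 41 cases. Exact error is the binomial tail at a true 50%.

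| Region | Cases | 95% limit: needs | Error | 98% limit: needs | Error |
|---|---|---|---|---|---|
| Prostate bed | 56 | 36 | 2.2% | 37 | 1.1% |
| Pelvis | 101 | 61 | 2.3% | 63 | 0.8% |
| Extrapelvic soft tissue | 90 | 55 | 2.2% | 57 | 0.7% |
| Bone | 41 | 27 | 3.0% | 28 | 1.4% |

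Chance of at least one false regional claim, if independent, is 1 − Π(1 − error): 9.4% with 95% limits and 4.0% with 98% limits. With 75 cases in every region it would be 1 − (1 − 0.0320)⁴ = 12.2% against 1 − (1 − 0.0101)⁴ = 4.0%.

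**4. The per-patient rule.** Read as an observed sensitivity of at least 70%, it needs 53/75 for one reader. P(X ≥ 53 | 75, 0.50) = 0.0002, far below 0.01. At a true 70%, P(X ≥ 53 | 75, 0.70) = 51%, against the 90% power stated for the test.

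**The case against.** Four arguments stand against this point.

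- **The adjusted test is in the document.** Section 8.2.1 says that the null will be tested, and 8.3.2 does not withdraw it. This stands: the test is absent from the analysis section, not from the plan.
- **The intervals are for reporting only.** Nothing in 8.3.2 says that a 95% limit will be compared with 50%, and unadjusted 95% intervals beside adjusted tests are ordinary practice. This stands in part. The inflation arises only if the limits are used as tests. But 8.3.2 does not call them descriptive and sets no adjusted test beside them, so for the regions they stand alone.
- **Trial success depends on the 70% rule.** This stands in full for the per-patient endpoint. A reader might infer that the trial's success claim is inflated, or quote the chance of a false claim over all five sensitivities: 1 − 0.975⁵ = 11.9% nominal, or 15.0% exact at 75 cases each. The documents do not support that. The per-patient claim is decided by a stricter rule into which no interval enters, so only the four regions belong in the count.
- **The regional error rate may mean little.** The region-level part of 8.3.2 leaves out regions without PSMA-positive disease, yet also defines false-negative regions. If the exclusion were applied literally, false negatives would drop out and regional sensitivity would approach 100% whatever the interval level. That is a separate problem. The figures here presume that false-negative regions are counted.

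**Conclusion.** The concern holds for the four regional sensitivities. The tests that determined the 75 cases are not in 8.3.2, and the only regional inference there is an unadjusted interval. If its lower limit is read against 50%, the chance of at least one false regional claim is about 9.4%, against 4.0% at the planned level; at 75 cases the error per region is 3.2% against 1.0%.

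These figures assume that true sensitivity is 50% in every region, that regions are independent, that the expected disease shares apply to the 375 patients with a reference standard, and that one reader is considered. The plan gives no correlation between readers, so a two-of-three rule was not modelled.

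It does not follow that per-patient success is too easy, or that the plan has no error control at all. The weakness is a missing link between two sections. It leaves the regional claims without a rule and gives the per-patient endpoint a success criterion different from the test for which it was powered.

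**What to change.** In 8.3.2:

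- State that the primary sensitivities (four regions and all regions combined) are each tested against 50% at one-sided 0.01, equivalently that the lower limit of the two-sided 98% Wilson interval exceeds 50%.
- Label the 95% intervals as descriptive.
- Apply the two-of-three-reader rule to each test, since readers are classified and reported separately.
- State how the per-patient test relates to the existing 70% rule: whether both must be met, or which one decides.

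The cost is a few sentences, written before the blinded reads are analysed. The decision intervals become about 19% wider (2.326/1.960 = 1.19). The sample size does not change: 75 cases still give 89.5% power under the 98% rule. A region that falls short of 75 cases, as bone would at an 11% share, will have less power at 0.01; that comes from the plan's use of an average 20% prevalence and is not created by this change.

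### The 90% power in 8.2.1 is for rejecting 50% sensitivity, but 8.3.2 decides success by a different and stricter 70% rule that is met only about half the time at a true 70%

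*Combined protocol and SAP*

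**What the plan says.** Section 8.2.1 sets up a hypothesis test: "the null hypothesis that the sensitivity is at most 50% will be tested against the alternative hypothesis that the sensitivity is greater than 50" per cent. It expects that the new scan "will substantially increase the sensitivity for the four regions to at least 70" per cent, and derives 75 diseased units (which it calls true positives) for rejecting 50% "with 90% power at the one-sided 0.01" level, the level being 0.05/5 to cover four regions and all regions combined. It then says that the planned accrual "will provide adequate power for detecting the anticipated improvement in the sensitivity for both the per-patient and per-region based" analyses, and that for the per-patient analysis "a sample size of 107 patients with biopsies/follow-up in total is sufficient". On the reference standard it says "we will combine imaging and biopsy follow-up in the primary aim".

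Section 8.3.2 reports sensitivity with two-sided 95% Wilson intervals and names no test against 50%. Its success condition is that "two of the three readers will need to have an 70% sensitivity for the detection of disease on a per patient level". The patients in whom this is judged are then listed in three parts: "for the cases that have a) imaging follow-up, b) pathology correlation or c) combination of pathology and imaging follow-up and/or pathology correlation". It does not say whether 70% is a point estimate or a confidence bound, or whether a), b) and c) are one set or alternatives.

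Section 8.3.1 assigns only patients with histopathology to the primary aim and sends all others to the secondary endpoints.

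**The concern.** The value assumed under the alternative in 8.2.1 has become the pass mark in 8.3.2. A test against 50% and an observed 70% in two of three readers are different decisions with different chances of success, and only the first has a stated power. A reader of 8.2.1 would take 90% as the chance that the trial succeeds if sensitivity is 70%. Under 8.3.2 it is not.

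The two criteria can also give opposite verdicts on the same data, and the plan does not say what follows then. The study is meant to support a marketing application (1.1), so which criterion decides, and in which patients, should be settled before the central reads.

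**Working it through.** **Inputs from the documents.** Null 0.50, alternative 0.70, one-sided 0.01, power 0.90, sizes 75, 107 and 375 (all 8.2.1); three readers, two needed, pass mark 70% (8.3.2).

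**Assumptions.** The 70% is an observed proportion of at least 70%. There is one case set. All three readers have the same true sensitivity. n is the number of disease-positive patients in that set. The documents do not give n for the per-patient analysis, so 75 to 375 is an illustrative range. Reader correlation is not given either.

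**Step 1: reproduce the 75.** Normal approximation:

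n = [(z(0.99)·√(0.5·0.5) + z(0.90)·√(0.7·0.3)) / 0.2]² = [(1.163 + 0.587)/0.2]² = 76.6.

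Power at n = 75 is 0.893. The stated 75 is within two patients of this, so it is accepted, and it belongs to the test against 50%. (The exact binomial test at n = 75 rejects from 49 upward, level 0.0053, power 0.843.)

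**Step 2: the rule in 8.3.2.** Let c be the smallest count with c/n ≥ 0.70 and q = P(X ≥ c) for X binomial(n, p). Two of three independent readers succeed with probability 3q² − 2q³.

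| n | c | true 70%: one reader / two of three | true 75% | true 80% |
|---|---|---|---|---|
| 75 | 53 | 0.507 / 0.510 | 0.842 / 0.933 | 0.981 / 0.999 |
| 107 | 75 | 0.539 / 0.559 | 0.899 / 0.971 | 0.995 / >0.999 |
| 375 | 263 | 0.503 / 0.505 | 0.986 / 0.999 | >0.999 / >0.999 |

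Over every n from 75 to 375, the two-of-three figure at a true 70% runs from 0.452 (n = 83) to 0.582 (n = 80). The variation comes from rounding of c. It does not rise with n, because the threshold equals the assumed truth.

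**Step 3: correlated readers.** Simulation with latent correlation from 0 to 0.95, at n = 75, 107 and 375, gives 0.50 to 0.57 at a true 70%. At a true 75% and correlation 0.95 it gives 0.85, 0.91 and 0.99.

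**Step 4: true sensitivity needed for a 90% chance under the rule** (two of three, independent): about 74.3% at n = 75, 73.3% at n = 107 and 72.0% at n = 375.

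**Step 5: disagreement between the criteria.** At n = 75 the exact test needs 49 (65.3%) and the rule needs 53 (70.7%). A result of 52/75 = 69.3% rejects 50% (exact one-sided p = 0.0005; lower limit of the 98% Wilson interval 56.0%) but fails the rule. The probability that one reader lands in this zone is:

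- n = 75 (49 to 52): 0.337 at a true 70%, 0.136 at a true 75%.
- n = 375 (211 to 262): 0.497 and 0.014.

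**Step 6: false success.** At a true 50% and n = 75, one reader meets the rule with probability P(X ≥ 53) = 0.0002.

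**Step 7: the population.** 8.2.1 combines biopsy and imaging follow-up for the primary aim, and 8.3.2 defines the primary analysis on the same combined standard. 8.3.1 restricts it to histopathology. These cannot all stand.

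**The case against.** The strongest reply is that 70% is the least favourable point of the hypothesis. 8.2.1 says at least 70%, and any threshold set at the assumed truth is met about half the time. The documents also hint at higher values. 8.2.1 reports 100% sensitivity on biopsy in the first cohort, and expects 24% of patients to have no disease on the scan. If all of those counted as false negatives and every positive scan were a true positive, sensitivity would be 76%. Treating the reported 87% as a positive predictive value (an assumption; 8.2.1 calls it specificity) gives 0.76 × 0.87 = 0.661 and 0.661/(0.661 + 0.24) = 73%. At n = 75 with independent readers the rule is then met with probability 0.81 (at 73%) to 0.96 (at 76%).

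This stands as a limit on the consequence. It does not remove the mismatch, because 70% is the value at which the 90% is claimed. The biopsy figure came from patients biopsied after a positive scan, with no false negatives or true negatives observed. 8.3.2 counts scan-negative patients with biochemical disease as false negatives, without settling how many enter the deciding set. The 73% to 76% is an illustration, not a forecast.

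A second reply is that a stricter benchmark on top of a powered test is no calculation error. That is right: the 75 reproduces, and 8.2.1 never claims 90% for the 70% rule. The defect is one of specification.

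A reader might also infer that the power falls short of 90% however a), b) and c) are read. The documents do not support that. If they are three chances and the two readers may pass in different sets, success at a true 70% and n = 75 reaches about 0.90 for imaging/pathology splits such as 17/58 or 20/55, against about 0.84 if both must pass in the same set. 8.3.2 states neither condition.

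**Conclusion.** The point holds as a mismatch between the stated power and the stated success rule. At a true 70% the two-of-three rule is met with probability 0.45 to 0.58 for n from 75 to 375, against the 90% given for the other test. This rests on three assumptions: an observed point estimate, one case set, and equal true sensitivity in all readers. Independence matters little at 70%; at 75% correlation lowers the chance somewhat. If a lower confidence bound above 70% were meant, success at a true 70% would be far rarer.

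Three stronger readings are not supported:

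- *The trial could wrongly declare success.* Against 50% the rule is very conservative.
- *The trial has a coin-toss chance overall.* That applies at the lower edge of the hypothesis; at a true 80% one reader passes with probability about 0.98 or more throughout the range.
- *375 is the most patients that can enter.* 8.2.1 makes 375 a requirement, not a ceiling, so the range shown is illustrative.

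The contradiction between 8.3.1 and the combined reference set is definite and leaves the deciding population open as well. It should be fixed; it does not call the sample size into question.

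**What to change.** 1. **8.2.1:** state that the 90% power applies only to the one-sided 0.01 test against 50%. Add a short table of the chance of meeting the two-of-three 70% rule at true sensitivities of 70%, 75% and 80%, at the expected number of disease-positive patients, with the reader correlation assumed.
2. **8.3.2:** state that 70% means an observed point estimate of at least 70% and that it decides primary success. Add the one-sided 0.01 tests against 50%, per patient and for the four regions, and give their role; otherwise the powered test has no place in the analysis. State before the reads that a), b) and c) form one combined case set, as the decision in 8.2.1 to combine imaging and biopsy indicates. The sponsor should confirm this, since the text says "or".
3. **8.3.1:** replace the histopathology-only population with that combined set.

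The cost is wording in three sections and one small table. Sample size and the 70% pass mark do not change. The downside is a less favourable stated chance of success near 70%. Making rejection of 50% the success criterion instead would relax the pass mark and is a separate decision for the sponsor.
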